6.2 Visit Window and Unscheduled Assessments

There is no visit window for the by visit analysis. Data will be analyzed according to the visit they are associated with. Data collected at unscheduled time points will not be summarized at the unscheduled time points. However, the unscheduled data will be used for analysis if data are missing at the next scheduled visit due to early termination.

6.3 Adjustment for Covariates

An exploratory analysis of the primary efficacy endpoint will be performed using a randomization-based approach (Dmitrienko and Koch 2017). This analysis will include age (categorical and continuous), gender, pooled site and baseline IA adjusted to 7 days as covariates.

6.4 Handling of Dropouts, Missing Data, and Data Discrepancies

For the primary analysis of the primary efficacy endpoint, the frequency of IA behaviors during the treatment (titration + maintenance) period will be calculated over the number of days with non-missing IA diary data in the treatment period. No explicit imputation of missing data will be used, but this approach is implicitly equivalent to using the frequency of IA behaviors during the days with non-missing IA diary data to impute the frequency for days after study discontinuation or days with missing IA diary data. In addition to this implicit imputation, multiple imputations under the assumption of missing at random (MAR) and missing not at random (MNAR) will be used for handling missing data for sensitivity analysis. Details of imputation methods are specified in Section 7.8.2

For analysis of frequency of IA behaviors during the treatment period (titration or maintenance), the following methods will be followed.

1) If subjects discontinued the study during or prior to the maintenance period, their maintenance period will be counted from Visit 5 (exclusive) through the date of last dose as documented on the End of Study eCRF page (inclusive). If the date of last dose is not collected, it will be imputed by the subjects' last visit for the study.

2) If subjects have \geq 7 daily diaries in the maintenance period, their maintenance IA frequencies will be based on maintenance daily diaries.

3) If subjects have <7 daily diaries in the maintenance period, their maintenance IA frequencies will be calculated pooling the titration period diaries with the maintenance period diaries.

4) If subjects do not have any maintenance diaries, their maintenance IA frequencies will be entirely derived from the titration period diaries.

Missing data for secondary efficacy endpoints (investigator CGI-S, investigator CGI-I and caregiver CGI-I) will be handled by using the Mixed Model for Repeated Measures method, which is implemented via SAS[®] PROC MIXED procedure. MMRM assumes data are "Missing At Random (MAR)". That is, the probability that an observation is missing may depend on the observed values but not the missing values in the previously scheduled visits.

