# 3.2 Overall Study Design and Plan

Protocol 810P301 is a randomized, placebo-controlled, double blind, multicenter, parallel group, fixed dose study to demonstrate the efficacy, safety, and tolerability of SPN-810 in the treatment of IA in patients aged 6-12 years with ADHD in conjunction with standard ADHD treatment. The study is presented schematically in Figure 1 and Figure 2. The study is divided into three phases: Pre-Treatment, Treatment, and Conversion/Taper.

Following screening, eligible subjects will enter a flexible baseline period, at which time the IA diary will be issued to the subject's primary caregiver. At the end of the baseline period, per the original plan, eligible subjects whose primary caregiver has maintained at least 80% compliance with the IA diary will be randomized to 1:1:1 to 18 mg/day SPN-810, 36 mg/day SPN-810, or placebo. However, based on the 810P301 study Interim Analysis result decision, the 18 mg arm was dropped partway through the study. As a result, subjects planned to be randomized to the 18 mg arm will be re-allocated to the 36 mg or placebo arm in a ratio of 2:1. A dose titration schedule will be followed, with dosing in the active treatment groups initiated at 3 mg/day and increased approximately every 3 days until the target dose is reached. After completing the two-week titration period and the three-week maintenance period, subjects will enter the conversion or tapering phase prior to discontinuing SM, at which time subjects will have the option to enter an open label extension (OLE) study. A subject who discontinues during the maintenance period prior to Visit 6 may be allowed to participate in the OLE on a case-by-case basis only after consultation between the Investigator, the Medical Monitor and the Sponsor. The OLE study will be conducted under a separate protocol. Subjects who choose to participate in the OLE will enter that study at a dose of 18 mg/day SPN-810.

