## 3.2.3 Conversion/Taper Phase

All subjects who complete the randomized, double blind portion of study 810P302 will have the option to participate in an OLE study (study protocol 810P304) in which all subjects will receive active SM treatment. Subjects choosing to participate will receive blinded conversion medication kits, and their total daily dose for the open label extension will be converted to 18 mg/day (Figure 1). Those subjects who do not elect to participate in this extension will be tapered off SM (Figure 2).

[figure not shown]
The 18 mg line in the 2 figures below will not be applicable to subjects re-randomized following the 810P301 interim analysis decision to drop the 18 mg dose.

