# 3.2.4 End of Study / Early Termination

Subjects will return to the study site for a final visit, after completing the 1-week Taper/Conversion Period. Those subjects who elect to continue in the OLE study will have procedures performed for that study as well. Subject who discontinues from the study during the maintenance period will be offered a Taper kit and will return to the study site for a follow-up visit (EOS). Subjects who discontinue during the titration period will not receive a taper kit and will only complete the EOS procedures.

Supernus ® Pharmaceuticals, Inc.	CONFIDENTIAL	
810P302	Version 7.0	Page 43 of 225

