# Based on the 810P301 study Interim Analysis result decision, the 18 mg dose arm was dropped partway through the study.

## 4.3.2 Identity of Investigational Product(s)

Test and reference (matching placebo) products are either purple (3mg) or yellow (9mg) round tablets printed on one side with the tablet dose strength (" $\underline{3}$ " or " $\underline{9}$ ") that will be supplied in labeled blister cards by the Sponsor. The Sponsor will package the SM in a double-blind configuration.

Each SM blister card will contain combinations of molindone extended-release and/or placebo tablets, which will supply a subject with 6 (six) to 8 (eight) days of dosing as well as some extras for lost product and/or to account for visit delays associated with patient/site schedules. The SM blister card types

include: Titration (two blister cards), Maintenance (three blister cards), Taper (one blister card), and Conversion (one blister card).

A single SM kit contains a total of 7 pre-packaged blister cards (two Titration blister cards, three Maintenance blister cards, one Tapering blister card and one Conversion blister card) and is marked with a unique 4-digit SM kit number.

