3.6 Changes to Analyses Planned in the Protocol

This SAP will be updated as necessary if any changes in the protocol occur due to the expected protocol amendment impacting the SAP.

4 **DEFINITIONS AND DERIVED DATASETS**

Table 1. Terminology and Definition

| Terminology | Definition |
|----------------------------|--|
| Study Medication | SPN-810 or the matching placebo. |
| Study Day | The first dose date (Day 1) is defined as the date on which a subject took the first dose of double-blind study medication (SM), Other study days are defined relative to the Study Day 1. For visits prior to the first dose of the SM, Study Day is calculated as Visit Date – Day 1. For visits after the first dose, Study Day is calculated as Visit Date – Day 1 +1. |
| Enrolled | Subject has provided signed informed consent. |
| Randomized | Subject is assigned with the kit number for the SM. |
| Completer for the Study | Subject who completes the maintenance period (Visit 6). |
| Baseline | Unless specified otherwise, baseline is defined as the non-missing value collected most recent to and before the time of the very first dose of the SM. For example, Visit 3 CGI-S, CHQ-PF28, PSI-4-SF, and SNAP-IV are collected prior to the first dose. Their values are considered baseline for the covariate analysis. |
| Baseline Period | For subject daily IA diaries, on and prior to Visit 3 (inclusive, ≤Day 1). |
| Prior Medication | Medication collected on the Prior/Concomitant Medication CRF, with the start date prior to Study Day 1. |
| Concomitant Medication | Medication collected on the Prior/Concomitant Medication CRF, with end date on/after Study Day 1. |
| Titration Period | For subject daily IA diaries from Visit 3 through Visit 5 (v3< to \leq V5) |
| Maintenance Period | For subject daily IA diaries from Visit 5 through Visit 6 (V5< to \leq V6) |
| Treatment Period | Titration and Maintenance Periods combined |

| Terminology | Definition |
|-----------------|--|

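### SAP 6.4 rule 1 can let taper-week or off-drug diary days into the primary endpoint for children who discontinue in maintenance, against the period definition in SAP 4

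*SAP*

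**What the plan says.** The SAP gives two end dates for maintenance. The terminology table in SAP 4 defines it as "For subject daily IA diaries from Visit 5 through Visit 6", and the treatment period is titration plus maintenance. SAP 6.4 rule 1, written for children who discontinue during or before maintenance, says instead that "their maintenance period will be counted from Visit 5 (exclusive) through the date of last dose", taking that date from the End of Study eCRF page. It adds: "If the date of last dose is not collected, it will be imputed by the subjects' last visit for the study". Rule 1 is introduced as applying to the treatment-period frequency, which is T in the primary endpoint (SAP 5.1) and also the basis of the two responder endpoints (SAP 5.2.2).

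The protocol determines what a last dose can be:

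- Section 4.3.2 lists the study-medication card types: "Titration (two blister cards), Maintenance (three blister cards), Taper (one blister card), and" Conversion (one blister card).
- Section 3.2.4: "Subject who discontinues from the study during the maintenance period will be offered a Taper kit". Children who stop in titration get no taper kit.
- Sections 4.2.7 and 4.6: early discontinuers complete Visit 7, and the diary device is collected at that visit.
- The conversion/taper phase lasts one week (Synopsis).

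SAP 4 defines study medication as SPN-810 or its placebo, with no exception for taper or conversion tablets.

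**The concern.** A completer's window closes at Visit 6, so T is measured on titration and maintenance dosing only. A child who stops after Visit 5, accepts the taper kit and keeps the diary has a last dose of study medication that is a taper dose. Rule 1 then counts the taper week as maintenance. If the last-dose date is missing, the window runs to the last visit, normally Visit 7, which can add days after all dosing has ended.

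The same endpoint would thus be measured over different kinds of days in completers and in maintenance discontinuers. Early discontinuers are the children whose data are most likely to be informative, and their number may differ by arm. The multiple-imputation analyses (SAP 7.8.2) would not necessarily correct this. Their third analysis week is the seven days after Visit 5, so taper diaries could enter it as observed values.

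**Working it through.** **1. The plan's own figure.** Inputs (Protocol 6.10, SAP 3.5): difference 15, SD 34.83, two-sided alpha 0.05, power 90%, attrition 20%. Noether's formula for the Wilcoxon rank-sum test:

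- P = Φ(15 / (34.83 × √2)) = 0.6196
- N = (1.960 + 1.282)² / (12 × 0.25 × (0.6196 − 0.5)²) = 244.7, or 122.4 per arm
- Power at 122 per arm = 89.9%
- 122 / 0.8 = 153 per arm, 306 in total

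The stated 122 and 306 are reproduced.

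**2. The two windows.**

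| Child | Window opens | Window closes | Taper/conversion week |
|---|---|---|---|
| Completer (SAP 4) | after Visit 3 | Visit 6 | excluded |
| Stops in maintenance (SAP 6.4 rule 1) | after Visit 3 | last dose, else last visit | not excluded |
| Stops in titration (rule 1) | after Visit 3 | undefined: no Visit 5 | no taper kit |

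**3. Share of T.** Assume 14 titration days, a stop on maintenance day k, a full 7-day taper and complete diaries. The taper share of the treatment period is 7 / (14 + k + 7).

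| k | Treatment-period days without taper | With taper | Taper share of T | Share of maintenance only, 7/(k + 7) |
|---|---|---|---|---|
| 1 | 15 | 22 | 32% | 88% |
| 7 | 21 | 28 | 25% | 50% |
| 20 | 34 | 41 | 17% | 26% |

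The last column, and the 7-diary threshold in rules 2 and 3, concern only the maintenance-only sensitivity analysis (SAP 7.8.2.3). There, at k = 1, the taper week raises the maintenance diary count from 1 to 8. The primary T pools all titration and maintenance days, so the threshold does not touch it.

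**4. How many children.** SAP 3.5 puts about 167 children before the change in randomisation. If they split 1:1:1, about 167 / 3 = 56 are in the untested 18 mg arm, leaving 306 − 56 = 250 in the tested arms. Twenty percent attrition gives 50. If one third to two thirds of those leave in maintenance (assumption), that is about 17 to 33 children, or 7% to 13% of 250. It is a ceiling, because it takes every one of them to use the taper kit and keep the diary.

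**5. Effect on the contrast.** Let p be the fraction of children who stop in maintenance and take the full week, s the taper share of T, and l the fraction of the treatment effect lost on those days. The diluted difference is 15 × (1 − p × s × l). The values of p and l are assumptions.

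| p | s | l | Difference | Power at 122 per arm |
|---|---|---|---|---|
| 5% | 17% (k = 20) | 50% | 14.94 | 89.7% |
| 10% | 23% (k = 10) | 100% | 14.66 | 88.6% |
| 20% | 32% (k = 1) | 100% | 14.05 | 85.9% |

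The last row is extreme: it needs all of the planned 20% attrition to fall on the first maintenance day, with a full taper each time.

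**The case against.** The strongest reply is that rule 1 points to a form that is not in the documents. If the End of Study field records the last maintenance dose, no taper day enters through the main rule. That stands as a limit, but the SAP does not say so. The protocol treats taper tablets as study medication, so a programmer would have to guess. The fallback to the last visit is a problem under either reading.

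It is also fair that the taper is offered, not required. Consent withdrawal and loss to follow-up are listed reasons for stopping (Protocol 6.5), and a full taper is unlikely then. IA diary review is scheduled only to Visit 6. The device also carries the dosing diary, so its collection at Visit 7 does not prove IA entries in the taper week. These points lower the count; they do not settle the definition.

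The per-protocol analysis requires completion of Visit 6 and so excludes every affected child. It is a partial check, but it is supplementary and drops all early discontinuers.

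A reader might infer that placebo children's days on active drug enter the primary endpoint. Protocol 3.2 does say "A subject who discontinues during the maintenance period prior to Visit 6 may be allowed to participate in the OLE on a case-by-case basis", and 3.2.3 says of children entering the extension that "their total daily dose for the open label extension will be converted to 18 mg/day". But conversion kits are described for children who complete the double-blind part and are dispensed at Visit 6. For early discontinuers the documents name only the taper kit, and the schedule figures are not shown. This is a possibility, not a finding.

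A reader might also infer that combined exposure in SAP 7.7.1 overruns in the same way. That section reports exposure by period, so no overrun is shown.

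**Conclusion.** The inconsistency is real: a stated rule in SAP 6.4 conflicts with the period definition in SAP 4 and bears on the primary endpoint. Read literally, it admits taper-week days, or off-drug days under the fallback, for children who stop after Visit 5, and excludes the corresponding week for completers.

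The size is modest. In an affected child, taper days are 17% to 32% of T, given a full taper and complete diaries. A reader might take 88% from the maintenance-only calculation as the weight in the primary endpoint; it is not. A reader might also take attrition on all 306 children; the untested 18 mg arm has to come out first, leaving at most about 17 to 33. Power moves from 89.9% to about 86-90% under the assumed ranges, and the shift is mainly toward the null if lost effect is the only mechanism. The documents do not support a claim of inflated efficacy.

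This should be fixed, chiefly because the end date of the primary window ought not to be chosen after unblinding.

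**What to change.** Before unblinding, reconcile SAP 4 and SAP 6.4 by stating that:

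- the treatment period ends at the earlier of Visit 6 and the last titration- or maintenance-phase dose;
- diary days on or after the first taper or conversion dose are excluded from T;
- if that dose date is missing, the fallback is the last pre-taper dose recorded in the dosing diary, or the discontinuation date, and not the last study visit;
- the same end date applies to children who stop in titration and have no Visit 5.

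If the End of Study field already means the last maintenance dose, say so in the SAP and change only the fallback.

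The cost is a few sentences, a change to one derivation, and a few fewer diary days for maintenance discontinuers. The protocol does not say that the dosing diary identifies which card a dose came from, nor does it schedule a dispensing date for an early discontinuer's taper kit. Check first whether the last pre-taper dose can be identified; if not, use the discontinuation date. No dosing or clinical procedure changes.

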6.4.1 Adverse Event or Concomitant Medications Dates or Times

For AEs with missing or partially missing start date/time, the following imputation rules will be applied for the determination of treatment-emergent status:

For partial start date/time:

- If the year is unknown, then the date will be assigned the date and time of first dose of study treatment.
- If the year is known to be different from the year of the first dose, then missing month and day will be imputed as the first month and first day of the month.
- If the year is known to be the year of the first dose,
 - a) If the month is unknown or is the same as the month of the first dose, then the missing month and day will be imputed by the month and day of the first dose.
 - b) If the month is known to be different from the month of the first dose, then the missing day is imputed as 01 (first day of the month).
- If the time is unknown, then:

- a) If the date (day, month, and year) matches the date of the administration of study drug, then the time of the study treatment will be used to impute the missing time.
- b) Otherwise, '00:00' will be assigned.

For the determination of the prior and concomitant status, the follow rules will be followed for incomplete dates.

- If the medication stop date is partially missing,
 - If the year and month indicate the stop date is before study drug administration, it is Prior medication.
 - Otherwise, it is concomitant medication.
- If the medication stop date is completely missing, it is concomitant medication.

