5.4 Safety Variables

5.4.1 *Medical History and Adverse Events (AEs)*

AEs that occur on/after signing ICF will be recorded on the AE CRF. Medical history and AEs will be coded for preferred term (PT) and system organ class (SOC) using Medical Dictionary for Regulatory Activities (MedDRA). AEs are evaluated by the investigators for seriousness, relationship, and severity.

5.4.2 *Prior, Concomitant, and Prohibited Medications*

Prior medications and concomitant medications will be extracted from the Prior/Concomitant Medication CRF. Medications taken prior to Study Day 1 will be considered as prior medications and medications taken on or after Study Day 1 will be considered as concomitant medications. Prior and concomitant medications will be coded using WHO Drug Dictionary (WHODD) for PT and Anatomical Therapeutic Chemistry (ATC) classification.

Prohibited medications include, but are not limited to,

- α_2 -adrenergic agonists (e.g. clonidine and guanfacine) used for any other reason except for monotherapy treatment for ADHD
- Anti-psychotics including aripiprazole, risperidone, quetiapine, and ziprasidone
- Anticonvulsants including carbamazepine and valproic acid, antidepressants, mood stabilizers including lithium, benzodiazepines, cholinesterase inhibitors or any drug known to inhibit CYP2D6 activity
- Herbal supplements

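### The rule for incomplete adverse event start dates ignores the stop date, so an event known to have ended before the first dose would be classed as treatment-emergent

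*SAP*

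**What the plan says.** SAP 6.4.1 opens the rule with its purpose: "For AEs with missing or partially missing start date/time, the following imputation rules will be applied for the determination of treatment-emergent status". The branches for the start date are:

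- Unknown year: "If the year is unknown, then the date will be assigned the date and time of first dose of study treatment".
- Known year other than the first-dose year: "then missing month and day will be imputed as the first month and first day of the month".
- First-dose year, first case, which applies when no month was recorded or it matches the dosing month: "then the missing month and day will be imputed by the month and day of the first dose".
- First-dose year, second case: "If the month is known to be different from the month of the first dose, then the missing day is imputed as 01".
- Missing time on a date that matches dosing: "then the time of the study treatment will be used to impute the missing time".

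None of these refers to the AE stop date, and nothing elsewhere in the protocol or SAP overrides them. Protocol 5.4.1.2 treats an AE as treatment-emergent if it starts on or after the first dose, or worsens after it.

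The documents disagree on when AE collection begins. SAP 5.4.1 states: "AEs that occur on/after signing ICF will be recorded on the AE CRF". The visit schedule (Table 1 in the protocol; SAP 3.2) has no AE mark at Visits 1 and 2 and starts at Visit 3. Protocol 4.2.3 makes the Visit 3 assessment post-dose. Protocol 5.4.1.2 starts questioning at Visit 3 but also asks for all AEs after enrollment. Protocol 6.13.1 speaks of AEs after randomization.

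**The concern.** Moving an uncertain start date to the first dose is a sensible cautious convention while the timing is in doubt. A recorded stop date before the first dose removes the doubt: the event began and ended untreated, and it cannot have worsened after dosing. The rule as written still classes it as treatment-emergent.

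At stake is the accuracy of the treatment-emergent tables in SAP 7.9.1, including the table of common events with its 5% threshold in any group. Double programming (SAP 8) would not necessarily catch the error, because two programmers who follow the same written rule reach the same wrong flag.

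**Working it through.** The plan states no figure for this rule, so there is none to reproduce. The check applies each branch to test dates and then sizes one misclassified case.

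**Inputs**
- Imputation branches: SAP 6.4.1.
- Treatment-emergent if start ≥ first dose: protocol 5.4.1.2.
- Pre-treatment phase of 45 days: SAP 3.3.2.
- Placebo arm of about 121: protocol 6.10.
- About 167 subjects randomized before the allocation change: SAP 3.5.
- Illustrative first dose: 20 June 2019 (assumption).

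**Branch test**

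| Recorded start | Recorded stop | Imputed start | Rule as written | With a stop-date condition |
|---|---|---|---|---|
| June 2019, day unknown | 10 June 2019 | 20 June 2019 | treatment-emergent | not |
| 2019, month and day unknown | 15 May 2019 | 20 June 2019 | treatment-emergent | not |
| year unknown | 15 May 2019 | 20 June 2019 | treatment-emergent | not |
| May 2019, day unknown | 10 June 2019 | 1 May 2019 | not | not |
| 2018, month and day unknown | 3 January 2019 | 1 January 2018 | not | not |

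The first three events are wrongly flagged, and a stop-date condition corrects all three. The last two are right either way. The defect is therefore confined to the unknown-year branch and the first case of the first-dose-year branch.

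**Reach.** Assume that pre-dose onsets are uniform over the window and first-dose dates uniform over 2017–2019.

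| Pre-dose window | Onset in the first-dose month (exposed if only the day is missing) | Onset in the first-dose year (exposed if month and day are missing) |
|---|---|---|
| 15 days | 74% | 98% |
| 30 days | 49% | 96% |
| 45 days | 33% | 94% |

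These are shares of pre-dose onsets. They are not counts of affected events: the documents give no number of pre-dose AEs or of incomplete dates.

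**Size of one false case**, as 1 / arm size:
- Placebo: 1/121 = 0.83 percentage points.
- 18 mg, assuming one third of 167: 167/3 ≈ 56, and 1/56 = 1.8 percentage points. As an illustration, one false case moves a preferred term from 2/56 = 3.6% to 3/56 = 5.4%, across the 5% threshold.

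These are upper values per event. SAP 7.9.1 counts a subject once per category, so a subject who also has a true treatment-emergent event under the same term adds nothing.

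**The case against.** The best defence is that the case is rare and the error is on the cautious side. It needs an event that ended before dosing, an incomplete start date, and a stop date complete enough to prove the end. If collection follows the visit schedules, few wholly pre-dose events enter the data. AEs are to be recorded immediately in source (protocol 5.4.1.2), and data are cleaned before lock (SAP 6.6). All of this stands and limits the size. It does not make the rule right for the events it reaches.

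Four stronger readings are tempting, and the documents do not support them.

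- *Pre-dose events with partial dates are to be expected.* They are only possible. SAP 5.4.1 allows them, but the schedules and protocol 4.2.3, 5.4.1.2 and 6.13.1 contain narrower wording.
- *The data will hold events that start after they stop.* SAP 6.4.1 limits the imputation to treatment-emergent status. Nothing says that the imputed date replaces the recorded one or feeds the duration in the AE listing.
- *The medication rule in the same section uses the stop date, so the AE rule contradicts it.* The SAP's definitions table sets concomitant status by the end date, whereas a treatment-emergent event is defined by its start or by worsening. The rules differ because the definitions differ.
- *The treatment comparison is biased.* The rule is identical across arms, and no differential effect follows from the text.

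**Conclusion.** Wrong as written, low severity. For two sets of incomplete start dates, SAP 6.4.1 gives the wrong treatment-emergent status to an event whose recorded stop date shows that it ended before the first dose. That conclusion follows from the text and needs no assumption about frequency.

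The practical effect is probably small and cannot be quantified from the documents. It depends on how many pre-dose AEs are captured, which the documents leave unsettled, and on how many of those have incomplete start dates. The per-case figures rest on the expected placebo arm size and on an assumed equal split of the 167 subjects randomized early.

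**What to change.** Add to SAP 6.4.1, before database lock:

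> Impute the start to the first-dose date only if the AE stop date is missing or does not show that the event ended before the first dose; if the available parts of the stop date show that it ended before the first dose, the event is not treatment-emergent.

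The SAP has no rule for partial AE stop dates, so the programming specification should add one line: a partial stop date shows a pre-dose end only if every date consistent with its recorded parts precedes the first dose. A stop recorded as June 2019 with a first dose on 20 June does not qualify, and the event stays treatment-emergent.

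Separately, reconcile the start of AE collection between SAP 5.4.1, the visit schedules and protocol 4.2.3, 5.4.1.2 and 6.13.1.

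The cost is one SAP sentence, one specification line and one condition in each of the two independently written programs. No safety information is lost: events with no stop date, or possibly ongoing at the first dose, remain treatment-emergent, and excluded events still appear in the listing of all AEs.
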